11.4 Return product analysis

Study Sponsor representatives and their contact information are provided in the Manual of Procedures (MOP) that accompanies this protocol.

Alcon products associated with device deficiencies and/or product related AEs should be returned and must include the Complaint # which will be provided by Study Sponsor after the case is entered in the iTrack (Sponsor's Medical Safety Database).

11.5 Unmasking of the Study Treatment

Not applicable; this study is open-label, unmasked study.

11.6 Follow-Up of Subjects with Adverse Events

The Investigator is responsible for adequate and safe medical care of subjects during the study and for ensuring that appropriate medical care and relevant follow-up procedures are maintained after the study.

The Investigator should provide the Study Sponsor with any new safety information (which includes new AEs and changes to previously reported AEs) that may affect the safety evaluation of the device. For AEs that are unresolved/ongoing at time of subject exit from

Document: TDOC-0054099 **Version:** 2.0; Most-Recent; Effective; CURRENT

Status: Effective Page 61 of 71

study, any additional information received at follow-up should be documented in the eCRF up to study completion (ie, database lock).

All complaints received after this time period will be considered and processed as spontaneous (following the postmarket vigilance procedures) and should be communicated to the medical device's manufacturer as per local requirements.

The Investigator should also report complaints on non-Alcon products directly to the manufacturer as per the manufacturer's instructions or local regulatory requirements.

11.7 Pregnancy in the Clinical Study

Pregnancy is not reportable as an AE; however, complications may be reportable and will be decided on a case—by-case basis. An Alcon form will be utilized to capture all pregnancy-related information until birth of the child.

12 ANALYSIS PLAN

12.1 Subject Evaluability

The final subject evaluability will be determined using the Deviations and Evaluability Plan (DEP) prior to locking the database.

12.2 Analysis Sets

All effectiveness analyses will be based on the full analysis set (FAS). All-implanted analyses set (AAS) will be used only for effectiveness analyses of monocular assessments.

All subjects with successful bilateral IOL implantation and have the bilateral measurements for defocus curve will be evaluable for the FAS.

All-implanted analysis set (AAS) is defined as all subjects with successful implantation of the test product in at least one eye.

The safety analysis set will include all patients with attempted IOL implantation (successful or aborted after contact with the eye).

12.3 Demographic and Baseline Characteristics

Demographics and baseline characteristics will be summarized for FAS,	AAS and safety
analysis set. Demographics include age, sex, ethnicity, height,	and race.

Document: TDOC-0054 099 **Version:** 2. o; Most-Recent; Effective; CURRENT

Status: Effective Page 62 of 71

Summaries of continuous variables will include the number of observations, mean, standard deviation, median, minimum, and maximum. Summaries of categorical variables will include count and percentage.

12.4 Effectiveness Analyses

This is a single aim descriptive study. No formal statistical hypothesis testing is planned for any endpoint. Rather the data will be summarized using descriptive statistics.

12.4.1 Analysis of Primary Effectiveness Endpoint

The primary effectiveness endpoint is:

• Binocular defocus cmve at 3 months (Visit 4A) post bilateral implantation

12.4.1.1 Statistical Hypotheses

No hypothesis testing of the primary effectiveness endpoint is planned.

12.4.1.2 Analysis Methods

The visual acuity data in logMAR for binocular defocus cmve at Month 3 will be summarized with the number of observations, mean, standard deviation, median, minimum, and maximum, two-sided 90% CI of the mean. A plot will be generated for the defocus curve with amount of defocus along the x-axis and logMAR visual acuity at each defocus along the y-axis.

12.4.2 Analysis of Secondary Effectiveness Endpoints

The secondal yeffectiveness endpoints are:

- Binocular defocus cmve at 1 month post-implantation (Visit 3A)
- Best conected binocula i visual acuity at distance (4 m) (Visits 3A, 4A)
- Unconected monocular & binocular visual acuity at 1 & 3 months post-implantation (Visits 3A, 4A) at 40 cm, 60 cm and 4 m
- Photopic best con ected binoculai contrast sensitivity with & without glare at 3 months post-implantation (Visit 4A)

Document: TDOC-0054099 **Version:** 2.0; Most-Recent; Effective; CURRENT

Status: Effective Page 63 of 71

• Subjective symptom questions at preoperatively and postoperatively: 3 months post-implantation (Visit 4A)

12.4.2.1 Statistical Hypotheses

No hypothesis testing of the secondaly effectiveness endpoints is planned.

12.4.2.2 Analysis Methods

The visual acuity data in logMAR for binocular defocus curve data at Month I will be summarized with the number of observations, mean, standard deviation, median, minimum, and maximum, and two-sided 90% CI of the mean. A plot will be generated for the defocus curve with amount of defocus along the x-axis and logMAR visual acuity at each defocus along the y-axis.

Best con ected binocular visual acuity at distance (Visits 3A, 4A), uncoffected binocular visual acuity at 40 cm, 60 cm and 4 m in logMAR (Visits 3A, 4A) will be summarized by visit with the number of observations, mean, median, standard deviation, minimum, maximum, and two-sided 90% CI of the mean. Additionally, these visual acuity endpoints will also be summarized in Snellen VA as categorical variables, by visit, with number of non-missing observations, cumulative frequency, and percentage in the following categories:

- 20/20 or better
- 20/25 or better
- 20/32 or better
- 20/40 or better

Unc01Tected mono cular visual acuity will be summarized in the same way as the uncon ected binocular visual acuity. The uncon ected monocular visual at 40 cm, 60 cm and 4 m will be summarized by the first and second operative eye for the following visits: Weeki, Month I and Month 3 for the full analysis set. Besides the FAS analysis, similarly, the uncon ected monocular visual acuity will be summarized for AAS as well.

[figure not shown]
Logarithmic contras t sensitivity for various spatial frequencies at Month 3 with and without glare will be summarized with the number of observations, mean, median, and standard deviation, minimum, maximum, and two-sided 90% CI of the mean. Plots will be generated separately for glare and without glare conditions with spatial frequency along the x-axis and mean logarithmic contrast sensitivity along the y-axis. Numberand percentage of subjects who do not have a record for a spatial frequency will be presented. Descriptive tables and

Document: TDOC-0054099 **Version:** 2.0; Most-Recent; Effective; CURRENT

Status: Effective Page 64 of 71

plots will be generated based on the scoring instructions of Vector Vision, and based on the observed data.

Subjective symptom questions will be summarized by visit (Preoperative, Month 3) per question with total number of non-missing observations, count in the category, and percent in the category.

12.5 Handling of Missing Data

No missing data will be imputed.

12.6 Safety Analyses

The safety endpoints are:

Document: TDOC-0054 099 **Version:** 2. 0; Most-Recent; Effective; CURRENT

Status: Effective Page 65 of 71

• Adverse events including secondary surgical interventions(SSis) related to the optical properties of the IOL.

- Device deficiencies
- Posterior capsule opacification
- Posterior capsulotomy
- IOL position change
- Intraocular pressure
- Surgical problems

Safety analyses will be made based upon the safety analysis set.

Rate of SSis related to the optical propeliies of the IOL for either eye will be summai ized by operative eye. All AEs will be coded using the Medical Dictionaly for Regulatoly Activities (MedDRA) and will be presented by severity (mild, moderate, or severe) and relationship to the study product. Ocular AEs will be summarized by operative eye. Descriptive tables (count and percentage) and listing will be generated for AEs based upon the categories of ocular and nonocular AEs, serious and non-serious AEs, as appropriate.

Device deficiencies will be listed. The count and percent of device deficiencies will be presented.

Results of posterior capsule opacification will be summarized with count and percentage in each categ01y by operative eye. A list of eyes with posterior capsule opacification will be presented.

Number and percentage of eyes with posterior capsulotomy will be presented by operative eye. A list of eyes with posterior capsulotomy will be presented.

Number and percentage of eyes with an IOL position change (tilted, decentered) will be presented by operative eye. A listing will be presented for eyes with IOL position changes.

Intraocular pressure and its change from baseline will be summarized descriptively with number of observations, mean, median, standard deviation, minimum, and maximum by operative eye. Baseline is defined as the last measurement taken prior to the IOL implantation. Individual listing of intraocular pressure and its change from baseline will be presented.

Document: TDOC-0054099 **Version:** 2.0; Most-Recent; Effective; CURRENT

Status: Effective Page 66 of 71

Count and percentage of eyes with surgical problems will be presented. Individual listings of surgical problems will be presented.

Results of slit-lamp exams, fundus exams, and other procedures at surgery, final incision size, lens information, IOL damage and IOL observations will be listed. If applicable, some of the items will not be listed as safety endpoints, e.g., final incision size without complications.

12.7 Interim Analyses and Reporting

Not Applicable. No interim analysis is planned for this study.

12.8 Sample Size Justification

Assuming a standard deviation of 0.17 logMAR for defocus visual outcomes, a sample size of 40 subjects will ensure more than 99% probability to observe the half width of 90% two-sided confidence interval to be not larger than 0.06 logMAR at a defocus point. The precision of estimates are within ±3 letters with visual outcomes.

Assume a dropout rate of 10% at Month 3, an approximate total of 44 subjects with intended bilateral IOL implantation are planned to be enrolled in the study to achieve 40 subjects with complete data at Month 3.

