Rate of SSIs related to the optical properties of the IOL for either eye during the study will be summarized by eye. All AEs will be coded using the Medical Dictionary for Regulatory Activities (MedDRA) and will be presented by severity (mild, moderate, or severe) and relationship to the test product. Device deficiencies, posterior capsule opacification, posterior capsulotomy, surgical problems, and IOL position change (tilt and decentration) will be summarized descriptively. Intraocular pressure at each visit and change from baseline will be summarized accordingly,

Assuming a standard deviation of 0.17 logMAR with defocus visual outcomes, 40 subjects will have more than 99% probability to observe the half width of 90% two-sided confidence interval will be no more than 0.06 logMAR at each defocus. The precision of estimates are within ± 3 letters with visual outcomes.

Assuming a dropout rate of 10% at Month 3, approximately 44 subjects will be bilaterally implanted to ensure that data for at least 40 subjects is available at Month 3.

Clinical trial duration

- a. Total expected duration of the clinical investigation: approximately 12 months
- b. Expected duration of each subjects' participation : approximately between 3 ~7 months

Alcon - Business Use Only Protocol - Clinical Effective Document: TDOC-0054099 Version: 2.0; Most-Recent; Effective; CURRENT Effective Date: 13-Dec-2017

Page 19 of 71 Status: Effective

	 c. Planned follow-up duration: about 3 – 4 months post 2nd eye implantation d. Enrollment period: approximately 5 months (The recruit period can be extended if 44 bilaterally implanted subjects cannot achieve 40 evaluable due to unilateral implantation or exclusion after screening visit.).
Key words	Prospective, Single Arm, Unmasked, Non-Randomized, Multi-Center Study, Cataract, Bilateral implantation, The ACRYSOF IQ PanOptix Presbyopia Correcting IOL, Model TFNT00, Trifocal, Korea
Associated materials	Biohazard labeled bag

.:; € □

a t, et

Inclusion/Exclusion

Administer Treatment(s) 0_hthalmic Assessments Distance VA at 4 m х9 х6 х6 Monocular Unconected xio Bino cular Uncon e cte d X Monocular Best X Conected Binocular Best X X X Conected Intermediate VA at 60 cm

Χ

Χ

Χ

Table 3-1	Schedule of Study Procedures and Assessments
	1 Operative Eye

		10	perative	Eye	2n _O	perati ve	Eye	Both	Eyes	

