8 STUDY POPULATION

The study population consists of adult Korean males and females, at least 20 years of age or older at the time of screening, with no ocular pathology that could confound study outcomes, who require cataract extraction in both eyes and desire an IOL that provides the potential for near, intermediate, and distance vision. Bilateral cataract extraction is planned in approximately 44 subjects in approximately 4 sites in Korea, with a target of 5 to 15 subjects per site. Site-specific targets may vary based upon individual site capabilities. Estimated time needed to recruit subjects for the study is approximately 5 months. The recruit period can be extended if 44 bilaterally implanted subjects cannot achieve 40 evaluable due to unilateral implantation or exclusion after screening visit. Assuming a 20% screening failure rate, approximately 55 subjects are expected to be enrolled.

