8.1 Inclusion Criteria

Written informed consent must be obtained before any study specific assessment is performed. Upon signing informed consent, the subject is considered enrolled in the study.

Document: TDOC-0054099 **Version:** 2.0; Most-Recent; Effective; CURRENT

Status: Effective Page 35 of 71

Subjects eligible for inclusion in this study must fulfill **all** of the following criteria (ocular criteria must be met in both eyes):

1.	Subject or legally authorized representative must be able to understand and sign an
	IRB/IEC approved Informed Consent form.
2.	Willing and able to attend all scheduled study visits as required per protocol.
3.	Adults, at least 20 years of age or older at the time of screening, of either gender in
	Korean, who require cataract extraction in both eyes.
4.	Clear intraocular media other than cataract in both eyes.
5.	Calculated lens power between +16.0 and +24.0 D.
6.	Preoperative OR expected postoperative regular corneal astigmatism of < 1.00 D.

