5.4 Interim Analysis for Safety

Not applicable.

6 Pharmacokinetic Analysis Strategy

Not Applicable.

7 Analysis Strategy for Other Endpoints

Not Applicable.

8 Sample Size and Power Calculations

Assuming a standard deviation of 0.17 logMAR for defocus visual outcomes, a sample size of 40 subjects will ensure more than 99% probability to observe the half width of 90% two-sided confidence interval to be not larger than 0.06 logMAR at a defocus point. The precision of estimates are within ± 3 letters with visual outcomes.

Assume a dropout rate of 10% at month 3, an approximate total of 44 subjects with intended bilateral IOL implantation are planned to be enrolled in the study to achieve 40 subjects with complete data at month 3.

9 References

None.

Printed By:

Printed By:

11 Appendix

[figure not shown]

Figure 1. Diagram of scheduled visits

Table 2. Study Plan

		1st (Operative	e Eye	2nd C	Operativ	ve Eye	Both	Eyes	
Visit	Visit 0 Day -60-0 Preoperative	Visit 00 ¹ Day 0 Operative	Visit 1 Day 1-2 Post Visit 00	Visit 2 Day 7-15 Post Visit 00	Visit 00A ² 2-30 Days Post Visit 00	Visit 1A Day 1-2 Post Visit 00A	Visit 2A 7-15 Days Post Visit 00A	Visit 3A 30-60 Days Post Visit 00A	Visit 4A ³ 90-120 Days Post Visit 00A	Unscheduled Visit
General Assessments and Pr	ocedur	es	1		1	1				
Informed Consent	Х									
Demographics	Х									
Medical History	Х									
Concomitant Medications	X X	Х	Х	Х	Х	Х	Х	Х	Х	Х
Urine Pregnancy Test ⁴	Х									
Inclusion/Exclusion	Х	Х			X					
Administer Treatment(s)		Х			X					
Ophthalmic Assessments				-						
Distance VA at 4 m										
Monocular				X ¹⁰			X ¹¹	X ⁶	X ⁶	
Uncorrected										
Binocular Uncorrected								Х	Х	
Binocular Best Corrected	Х							Х	Х	
Intermediate VA at 60 cm					•					
Monocular Uncorrected				X ¹⁰			X ¹¹	X ⁶	X ⁶	
Binocular Uncorrected								Х	X	
Near VA at 40 cm										
Monocular Uncorrected				X ¹⁰			X ¹¹	X ⁶	X ⁶	
Binocular Uncorrected								Х	X	
Lighting measurements	X			X			X	Х	X	
Binocular Defocus Curve								X	X	

Document: TDOC-0054036 Status: Effective

Version: 2.0; Most-Recent; Effective; CURRENT

		1st (Operative	e Eye	2nd (Operativ	ve Eye	Both	Eyes	
Visit	Visit 0 Day -60-0 Preoperative	Visit 00 ¹ Day 0 Operative	Visit 1 Day 1-2 Post Visit 00	Visit 2 Day 7-15 Post Visit 00	Visit 00A ² 2-30 Days Post Visit 00	Visit 1A Day 1-2 Post Visit 00A	Visit 2A 7-15 Days Post Visit 00A	Visit 3A 30-60 Days Post Visit 00A	Visit 4A ³ 90-120 Days Post Visit 00A	Unscheduled Visit

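### Does the sample-size statement (44 planned, 40 at Month 3, over 99% precision) fail on its own figures?

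*Protocol*

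**What the plan says.** Protocol Section 12.8 starts from a planning SD: "Assuming a standard deviation of 0.17 logMAR for defocus visual outcomes". On that basis "a sample size of 40 subjects will ensure more than 99% probability" that the half-width of the two-sided 90% CI is at most 0.06 logMAR, stated for a single defocus point. With 10% dropout at Month 3, "an approximate total of 44 subjects with intended bilateral IOL implantation are planned to be enrolled in the study", the aim being 40 with complete data. SAP Section 8 repeats this: "an approximate total of 44 subjects with intended bilateral IOL implantation are planned to be enrolled in the study to achieve 40 subjects".

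The Protocol Summary (Section 3) words both parts differently. On numbers it says "approximately 44 subjects will be bilaterally implanted to ensure that data for at least 40 subjects is available at Month 3". On precision it says that the "confidence interval will be no more than 0.06 logMAR at each defocus".

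Protocol Section 8 plans bilateral extraction in about 44 subjects and adds: "Assuming a 20% screening failure rate, approximately 55 subjects are expected to be enrolled". Section 8.1 defines the term: "Upon signing informed consent, the subject is considered enrolled in the study". Sections 3 and 8 also let recruitment be extended if 40 evaluable subjects are not reached because of unilateral implantation or exclusion after screening.

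No hypothesis test is planned (Protocol 12.4, SAP 4.2). The CIs are t-based (SAP 4.3) and reported defocus point by defocus point (SAP 4.3.1).

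**The concern.** With no hypothesis test and no success criterion, the precision statement is the only quantitative justification of the trial's size, so it ought to hold. Three features invite doubt.

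- **Dropout.** 44 × 0.90 = 39.6, short of 40. Dividing instead, 40 / 0.90 = 44.4, which rounds up to 45.
- **Population label.** Enrolment is defined as signing consent, and Section 8 expects 55 such subjects. Section 12.8 and SAP Section 8 nevertheless apply the word to 44. Taken literally, 44 consented would leave 44 × 0.8 × 0.9 = 31.7 evaluable, and the precision claim would fail.
- **Number of points.** The curve runs from +2.00 D to −5.00 D in 0.50 D steps (Protocol 10.2.10), which is 15 points. If the synopsis meant that all 15 half-widths stay within 0.06 together, over 99% would be too high.

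At stake would be a trial smaller or less precise than its own justification says.

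**Working it through.** **Inputs.** SD 0.17 logMAR, half-width limit 0.06, n = 40, 10% dropout, about 44 planned (Protocol 12.8, SAP 8); t-based two-sided 90% CI (SAP 4.3); 20% screen failure and 55 enrolled (Protocol 8); 15 defocus points (Protocol 10.2.10).

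**1. The plan's own precision figure.** Half-width = t(0.95, n−1) · s / √n. It is at most 0.06 when s ≤ 0.06√n / t, so

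P = P[χ²(n−1) ≤ (n−1) · (0.06√n / (0.17 t))²].

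At n = 40: t = 1.685, so s may reach 0.06 × 6.325 / 1.685 = 0.2252. The χ² limit is 39 × (0.2252 / 0.17)² = 68.45, and P = 0.9975. The claim of over 99% reproduces. The half-width at s = 0.17 is 0.045. At 0.02 logMAR per letter (an assumption), 0.06 is 3 letters, as stated.

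**2. How many completers the claim needs.**

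| n | P(half-width ≤ 0.06) |
|---|---|
| 37 | 0.989 |
| 38 | 0.993 |
| 39 | 0.996 |
| 40 | 0.9975 |

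The smallest n that keeps the claim above 99% is 38, two below the target.

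**3. Dropout from 44.** Treat completers as Binomial(44, 0.90). The mean is 39.6, P(at least 40) = 0.547 and P(at least 38) = 0.854. Averaging the precision probability over this distribution, Σ P(X = k) · P(half-width ≤ 0.06 | n = k) = 0.995. The claim therefore survives random 10% dropout. The figure 44 is what 40 × 1.10 gives; the division 40 / 0.90 gives 45. The difference is one subject in a number labelled approximate.

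**4. 44 against 55.** 55 × 0.80 = 44 and 44 × 0.90 = 39.6. The chain of 55 consented, 44 for implantation and about 40 completing is exact at the first step and rounds at the second. If 44 were the number consented, completers would be Binomial(44, 0.72) with median 32; the precision probability is 0.926 at n = 32 and 0.895 averaged over attrition. That reading requires setting Section 8 aside. It also sits badly with Section 12.8, which qualifies its 44 by intended bilateral implantation.

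**5. Fifteen points.** At n = 40 each point separately has probability 0.9975. Jointly, independence gives 0.9975¹⁵ ≈ 0.964, and simulation with a common correlation of 0.9 gives about 0.99. The documents give no between-point correlation. At n = 39, independence gives 0.9958¹⁵ = 0.939. These are answers to a question the plan does not ask: one passage speaks of a defocus point and the other of each defocus, and both describe points one at a time.

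**The case for a change.** The strongest case for a change rests on two points. First, by the protocol's own definition, 44 enrolled and 55 enrolled cannot both be right, and SAP Section 8 gives neither the 55 nor the 20% screen-failure rate, so a reader of that section alone cannot rebuild the chain. Second, promising at least 40 from 44 implanted is too strong when the chance is 0.547. The extension clause does not rescue it, because it covers unilateral implantation and exclusion after screening but not ordinary dropout after bilateral implantation.

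Both observations are correct as criticism of wording. Neither reaches the design. The SAP is read with the protocol, where Section 8 and the synopsis settle which population the 44 describes. A shortfall to 39 or 38 completers leaves the per-point precision above 99%, so missing the round number 40 by one or two costs nothing that the plan claims.

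The request for a joint statement over 15 points does not stand. The analysis is descriptive and pointwise, and any joint figure would depend on a correlation the documents do not supply. A range such as 95–98% at n = 39 could not be written in as fact: independence alone gives 93.9%.

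One may also note that the claim depends on the SD: at n = 40 it holds up to about 0.178 and falls to 88% at 0.20. That varies a declared planning assumption. Nothing in the documents shows 0.17 to be wrong, so it is not an arithmetic fault.

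**Conclusion.** The sample-size statement delivers its figures. The precision claim is 99.75% at n = 40, stays above 99% down to 38 completers, and is 99.5% averaged over 10% dropout from 44. The counts 55, 44 and about 40 agree.

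Two clerical slips remain: the word enrolled for the 44 in Protocol 12.8 and SAP 8, and the synopsis's promise of at least 40 where 39.6 are expected. Tidying them at a convenient revision would be harmless, but it would change no recruitment target, analysis, precision claim or conclusion, so no change to the plan follows.

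This rests on the planning SD of 0.17 at each point, approximately normal data, independent dropout at 10%, and reading the 44 as the subjects going to bilateral implantation, as Protocol Section 8 and the synopsis describe them.
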